Research Repositories: If the purpose of this submission is to establish a Research Repository (bank, registry) indicate whether the material you plan to collect would or would not be available from a commercial supplier, clinical lab, or established IRB approved research repository. Provide scientific justification for establishment of an additional repository collecting duplicate material. Describe the repository design and operating procedures. For relevant information to include, see the UK Research Biospecimen Bank Guidance [\[PDF\]](#) or the UK Research Registry Guidance [\[PDF\]](#)

Patient recruitment will be done for the first 42 months of the study after administrative startup (Figure 2). Biochemical measurements, MDCT, QCT and DXA scans, and clinical assessment will be performed at baseline, 6 months, and at 12 months, 18 months and 24 months. Treatment monitoring visits with blood draws (initially bi-weekly or monthly and thereafter every 3 months) and adverse event monitoring phone calls (monthly at least) will occur during years one through five. Interim analyses and first publications will be done once 50% of patients have completed 1 year visits, approximately at the end of Year 3. Final analyses of the data and preparation of abstracts and manuscripts of the obtained results will be completed during year 5. Control patients who completed 1 year of follow up without treatment will be offered additional 2 years of enrollment with treatment according to protocol. Patients who were initially randomized to treatment groups will be offered continued treatment for an additional 1 year to complete 2 years of therapy. Previously enrolled patients will be recruited from the beginning of patient enrollment. These patients will be provided with an additional consent for the extension of the treatment arm.

Figure 2: Study Timeline

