- Inability to stand or sit upright for at least 30 minutes;
- Treatment within the past 6 months with drugs that may affect bone metabolism including bisphosphonates and teriparitide (except for treatment with calcitriol, Vit D analogs and/or calcimimetics).
- Abnormalities of the esophagus which delay esophageal emptying such as stricture or achalasia;
- Calcidiol levels below the normal range. The current routine clinical practice in our dialysis clinics is to check calcidiol status twice yearly and supplement with vitamin D according to serum calcidiol levels. It is therefore unlikely that a substantial number of patients will be excluded due to this exclusion criterion.

Attachments

Subject Recruitment Methods & Privacy: Using active voice, describe plans for the identification and recruitment of subjects, including how the population will be identified, and how initial contact will be made with potential subjects by those having legitimate access to the subjects' identity and the subjects' information.

Describe the setting in which an individual will be interacting with an investigator or how and where members of the research team will meet potential participants. If applicable, describe proposed outreach programs for recruiting women, minorities, or disparate populations as participants in clinical research. Describe steps taken to minimize undue influence in recruiting potential participants.

Please note: Based upon both legal and ethical concerns, the UK IRB does not approve finder's fees or "cold call" procedures made by research staff unknown to the potential participant.

For additional details, see topic "Recruitment of Subjects/Advertising" on ORI's [IRB Survival Handbook web page](#) and the PI Guide to Identification and Recruitment of Human Subjects for Research [\[PDF\]](#).

Subject Recruitment Methods and Privacy: The study coordinators will visit the patients at the dialysis clinics during their regular treatment hours. The nephrologists at these clinics have worked with us on previous research activity and are willing to cooperate. Patients will be informed about the goals and the protocol of the study. An IRB approved recruitment flyer will be given to patients who are interested in participating in the study. A list of screened patients will be kept under lock and key in the study coordinators' office and on a password protected computer.

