The study coordinators will approach via phone during normal business hours all patients who completed study participation and those currently enrolled in ROD III to discuss the extended enrollment option. All previous patients will be eligible for approaching for the extension regardless of when initial participation was completed. Patients will be informed about the goals and the protocol of the study. A list of screened patients will be kept under lock and key in the study coordinators office and on a password protected computer.

Advertising: Specify if any advertising will be performed. If yes, please see ["IRB Application Instructions - Advertisements"](#) for instructions on attaching copies of the information to be used in flyers or advertisements. Advertisements must be reviewed and approved by the IRB prior to use. For additional details, see topic "Recruitment of Subjects/Advertising" on ORI's [IRB Survival Handbook](#) web page for the *PI Guide to Identification and Recruitment of Human Subjects for Research* [D7.0000] document [\[PDF\]](#). If you will be recruiting subjects via advertising at non-UK owned or operated sites, you should include a copy of written permission from that site to place the advertisement in their facilities.

Note: Print and media advertisements that will be presented to the public also require review by [UK Public Relations \(PR\)](#) to ensure compliance with UK graphic standards, and equal opportunity language. [i](#)

Print advertisements: The study may recruit subjects through flyers, brochures, posters, cards for clinic rooms, Research Spotlights, bookmarks placed on campus and in the surrounding community and region, including but not limited to the UK Medical Center, UK Clinics, Good Samaritan Hospital, student center, UHS, the 5 UK Center for Clinical and Translational Research wall mounts, Cardinal Hill, monitor screens, and area facilities and businesses.

This study may use physician referral letters to community physicians for patient recruitment.

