Patients consenting for baseline measurements will have BMD measurements of the total hip, lumbar spine and radius by DXA and total body scan. We do not use QCT for initial BMD assessment to avoid unnecessary radiation exposure to patients with normal bone mass who will be excluded from the study. Patients who are not do not have low bone densityosteoporotic by DXA T-scores/Z-

scores at any site will be excluded from further participation. Results from our prior funding period study indicate this will be 30% or 178 patients. Those patients who are identified as having low bone density/osteoporotic will have blood draws performed for determination of turnover status (PTH, PTH ratio and TRAP-5b; see Table 1) and baseline biochemical results (serum calcium and BSAP). They will also have BMD measurements of the total hip and spine by QCT, and CAVC measured by MDCT. Patients will be assigned to one of two treatment arms based on their turnover status: 1) low turnover patients and 2) normal or high turnover patients. For each treatment arm we will use adaptive randomization by group completion rates, age race and gender to assign patients to one of two groups A) treatment, and B) no study treatment (standard of care) controls.

For the extension of treatment modification, we will contact all patients who completed one year in either the treatment or control arms. Patients who previously participated in the treatment arm will be offered an additional 1 year of therapy to complete 2 years of therapy. For patients who previously participated in the control arm, they will be offered 2 years of therapy. Both therapies can be given in two consecutive years, or with a time-gap in-between.

TREATMENT PROTOCOLS:

Low Turnover Groups: Patients with low bone turnover will be randomized to receive daily teriparatide injections with cinacalcet or no study treatment, i.e. standard of care, as controls.

Normal or High Turnover Groups: Patients with normal or high bone turnover will be randomized to receive alendronate or no study treatment, i.e., standard of care, as controls. Teriparatide is not justified in these patients because it might worsen underlying high turnover abnormalities and requires avoidable daily injections.

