The major concern regarding teriparatide treatment is the potential risk for osteosarcoma. There is increased baseline risk for osteosarcoma in patients with Paget's disease of bone, pediatric populations and young adults with open epiphyses, or prior external beam or implant radiation therapy.⁵⁹ In male and female rats, teriparatide caused an increase in the incidence of osteosarcoma that was dependent on dose and treatment duration. This is why the FDA has limited administration of the drug to a maximum of two years. The observed effect in rats was found with systemic exposures ranging from 3 to 60 times the exposure in humans given a 20 µg dose. The spontaneous occurrence of osteosarcoma in the general population is 1:400,000. At this time, per the manufacturer, more than 1.2 million patients have been treated with teriparatide and three cases of osteosarcoma have been reported.

Cinacalcet is approved for CKD-5D patients. In a double blind placebo controlled trial of cinacalcet in 3,861 patients, there were no differences in serious or non-serious adverse events among the over 1,000 events tracked. This drug is routinely used in daily practice to treat CKD-5D patients for hyperparathyroidism. It may induce hypocalcemia.

The risks associated with blood draws are minimal and restricted to potential discomfort during the procedure and, possibly, soreness, bruising, pain and bleeding at the venipuncture site. In addition, there is a possibility that the patient will faint.

All CT and DXA involve patient exposure to ionizing radiation, but both DXA and CT are generally considered to be safe with relatively low radiation exposure to the patient. Doses involve exposure to the chest, abdomen, and the pelvic region. The yearly safety threshold given by the United States Nuclear Regulatory Commission for occupational radiation exposure is 50 mSv.⁷³ The radiation dose from a typical DXA bone scan produces approximately 1/300th of the natural background radiation dose we receive each year. This radiation dose would not be considered a risk of producing any harmful effects. Each CT scan will give a radiation dose greater than that from typical natural background exposure, but less than the limit for radiation workers and well below the levels that are considered to be a significant risk of any harmful effects.

[Back to Top](#)

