Treatment Consent Once bone turnover status has been determined, patients will be approached for the second consent form addressing treatment. It will again be emphasized that willingness or unwillingness to participate in any aspect of the proposed studies will not affect the patients' medical care. The protocol will be presented by the study coordinators supported by the PI where needed and the patients will be given ample time to think about their participation and to discuss participation with their primary nephrologist, other treating physicians, or any other persons. After agreement to participate, the second written treatment consent form approved by the IRB of the University of Kentucky will be signed by each patient. One copy of the first and second signed consent form will be given to the patient; another will be kept in the study coordinators' office under lock and key.

Expanded Consent Patients who have previously completed one year of therapy or standard of care or are currently enrolled will be re-approached for a third consent to extend the treatment so that two years of medication therapy will be completed. The same standard of informed consent will apply to the treatment extension consent.

Protection against risks The PI is a nephrologist who specializes in bone and mineral disorders and renal osteodystrophy. All personnel involved in the research have passed or will pass the test "Protection of Human Subjects in Research," by the Collaborative Institutional Training Initiative (CITI) at the University of Miami. All investigators and key personnel have received or will receive training for the Health Insurance Portability and Accountability Act (HIPAA) (levels 1 and 2).

Monthly and quarterly monitoring: Monthly telephone or personal contact will be made by the study coordinators to the patients in order to monitor possible adverse events or reactions. Thereafter, every three months, patients will be seen by the study coordinators who will perform a general health assessment. At these monitoring visits, there will be blood draws for monitoring safety. The PI will be available at all times for phone consultation via cell phone and/or a 1-800 telephone number of the University of Kentucky Healthcare written on the consent forms.

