Teriparatide for patients with low bone turnover: Patients with increased baseline risk of osteosarcoma will be excluded from this study (Paget's disease of bone, pediatric populations and young adults with open epiphyses, or prior external beam or implant radiation therapy). Our inclusion/exclusion criteria eliminate all of these patients. There are no direct contraindications given for CKD patients given in the package inserts and the safety web page. However, because bone loss with CKD-5D is not specifically addressed in the indications, we have obtained an IND (Investigational New Drug) from the FDA.

If during the monthly monitoring calls/visits or quarterly visits patients complain of new onset adverse reactions such as arthralgia, pain, nausea, dizziness or leg cramps, the patients will be counseled regarding standard treatment measures. Follow-up contact will be made in one week and if symptoms persist, treatment will be discontinued until the next regularly scheduled quarterly monitoring visit. Follow-up communication will occur within 1 week +/- 3 days and if problems persist despite discontinuation, patients will be referred to his/her primary care provider.

If patients complain of injection site reactions, they will be counseled regarding their injection technique and follow-up contact will be made in one week +/- 3 days. If reactions persist, treatment will be discontinued until next regularly scheduled quarterly monitoring visit. If problems persist despite discontinuation, patients will be referred to his/her primary care provider and their participation in the study will end.

In the rare case where PTH level maintenance requires cinacalcet doses that induce serum calcium levels below 8.5 mg/dL, treatment will cease and patients will be excluded from further participation in the study.

Alendronate for patients with normal or high bone turnover: Our inclusion/exclusion criteria cover all of the above-mentioned contraindications. To be safe, we have obtained an IND from the FDA.

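### The extension uses the whole two-year teriparatide maximum that the plan cites, and no visible rule counts teriparatide taken before entry or during a gap (minor safety safeguard)

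*Combined protocol and SAP*

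**What the plan says.** All references are to the combined protocol and SAP.

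- **Potential Risks.** Osteosarcoma is named as the main concern with teriparatide. In rats it depended on dose and on length of treatment, and the text continues: "This is why the FDA has limited administration of the drug to a maximum of two years". It does not say whether the two years are per course or cumulative.
- **Study Population, exclusion criteria.** The one rule on earlier use is "Treatment within the past 6 months with drugs that may affect bone metabolism including bisphosphonates and teriparitide".
- **Study Design.** "Control patients who completed 1 year of follow up without treatment will be offered additional 2 years of enrollment with treatment according to protocol". Patients first randomised to treatment are offered one further year, making two.
- **Research Procedures.** The same offers are repeated, with "Both therapies can be given in two consecutive years, or with a time-gap in-between".
- **Subject Recruitment Methods and Privacy.** "All previous patients will be eligible for approaching for the extension regardless of when initial participation was completed".
- **Safety Precautions, Expanded Consent.** Patients "will be re-approached for a third consent to extend the treatment so that two years of medication therapy will be completed".
- **Safety Precautions, teriparatide.** "Patients with increased baseline risk of osteosarcoma will be excluded from this study". The listed risks are Paget's disease, open epiphyses and radiation. Earlier teriparatide is not among them.
- **Research Materials, Records and Privacy.** Medical history is recorded. The therapies named are phosphate binders, vitamin D and calcimimetics, and no exposure limit is attached to any of them.

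**The concern.** A limit justified by duration of exposure is most naturally read as a limit on total exposure. The extension uses all of it. A 6-month washout shows whether a patient took the drug recently, not how much the patient has ever taken. A former user could therefore meet every visible criterion, complete the full course and pass the maximum that the plan itself gives as its safety basis. The same could happen to a patient who takes teriparatide outside the study between the first year and the extension.

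Former users are plausible in this recruitment area. The Background describes six patients given teriparatide with cinacalcet for up to six months. The start of that sentence is missing, but the context suggests they were this team's patients. Potential Risks adds that the principal investigator has used these drugs for more than ten years in patients with and without CKD.

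What is at stake is a safety safeguard in the low-turnover arm only. Randomisation, the endpoints and the alendronate arm are not affected.

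**Working it through.** **Inputs from the plan**
- Cited maximum: 24 months (Potential Risks).
- Study treatment: 12 months plus 12 more for treated patients; 24 for former controls (Study Design, Research Procedures).
- Holds: two weeks for serum calcium above 11.0 mg/dL (Treatment Protocol for Teriparatide); until the next quarterly visit for persistent symptoms (Safety Precautions).
- Human figures: three osteosarcoma cases in more than 1.2 million treated patients; "The spontaneous occurrence of osteosarcoma in the general population is 1:400,000".

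**Inputs assumed.** P is months of teriparatide taken outside the study. The documents give no value, so a range is shown.

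**Step 1: the plan's own figure.** Treated: 12 + 12 = 24. Former controls: 0 + 24 = 24. The stated two years is reproduced. Headroom = 24 - 24 = 0 months.

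**Step 2: total exposure.** Total = 24 - H + P, where H is months withheld and not made up. The total exceeds 24 only if P > H. A two-week hold is 14/30.44 = 0.46 months.

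| Assumed P (months) | No hold | One two-week hold | One hold of up to 3 months |
|---|---|---|---|
| 3 | 27 | 26.5 | 24 |
| 6 | 30 | 29.5 | 27 |
| 12 | 36 | 35.5 | 33 |
| 24 | 48 | 47.5 | 45 |

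P = 6 corresponds to the longest treatment described for the six patients in the Background. The larger values only show how the formula behaves.

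**Step 3: what a cumulative cap would allow.** Study months = max(0, 24 - P), so P = 3, 6, 12, 24 gives 21, 18, 12, 0. The randomised first year stays whole if 12 + P <= 24, that is, P <= 12.

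**Step 4: human risk on the plan's figures.** 1,200,000 / 3 = 400,000, or 1 in 400,000. This equals the quoted spontaneous occurrence. The time bases of the two figures are not given.

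**The case against.** The strongest reply is that everything depends on the word cumulative, which the plan does not use. If the maximum is per course, nothing remains, because study treatment stops at 24 months. The documents that could settle this (the prescribing information, the study drug form, the FDA correspondence on the IND and the consents) are attached but not shown, and one of them may already carry a cap. This stands. It is why the point is conditional and says no visible rule.

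Second, outside use is hypothetical. The Background says bone loss in these patients is seldom treated, recent users are excluded at entry, and medical history might reveal earlier use. This limits the number affected. It does not supply a rule that acts on what the history shows.

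Third, dose reductions and holds lower exposure. Holds are netted out above: a three-month hold absorbs P = 3 but not P = 6. Injecting on 5 of 7 days lowers the dose, not the calendar duration.

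A reader might infer three stronger things that the documents do not support:

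- **That the extension itself breaches the limit.** It does not. It is built to total two years, and the first study year still counts after a gap.
- **That entry criteria lapse at the extension.** The recruitment section makes past patients eligible to be approached, not to be dosed. It neither states nor rules out a recheck.
- **That long gaps show outside use.** Enrolment began in January 2015, so the earliest completers finished about January 2016. The extended-treatment consent on file is dated September 2019, about 44 months later. That is time available, not evidence that anyone took the drug.

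**Conclusion.** The point holds as a minor safeguard that is worth adding. On the cumulative reading, the visible eligibility and extension rules, followed exactly, would let a former or gap-period user receive up to 24 + P months, less any holds: 30 months for P = 6 with no hold. This rests on two assumptions, that the maximum is cumulative and that some patients have P > 0. The documents confirm neither. The number affected is not given and is probably very small.

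It would be wrong to present this as a demonstrated human hazard. The plan's own figures show no excess over the spontaneous occurrence, and the rat findings arose at 3 to 60 times human exposure. The case for acting is narrower: the plan cites a limit, uses all of it, and shows no step that would keep a former user inside it.

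**What to change.** 1. **Potential Risks:** state that the two-year maximum is applied cumulatively. If the attached prescribing information, IND correspondence or consents already contain a cap, copy it into the rules below.
2. **Exclusion criteria:** keep the 6-month washout; excluding every past user is not needed. Record lifetime teriparatide months (P) before randomisation in both low-turnover groups, because controls are later offered the drug. Make patients with P above 12 ineligible for the low-turnover randomisation, so that the cap never truncates the randomised year.
3. **Research Procedures and Expanded Consent:** before the extension consent, ask again about teriparatide taken outside the study, add it to P, and re-apply the washout to outside use. Word the washout so that study teriparatide does not count against patients who continue without a gap.
4. **Treatment Protocol for Teriparatide:** limit study teriparatide to 24 - P months and stop at 24 cumulative months. After a full first year without holds, a treated patient with P = 6 would have 24 - 6 - 12 = 6 extension months; a former control with P = 6 would have 18.

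The cost is one history item asked twice, one eligibility line and one stop rule. The downside is that a very few patients get a shorter extension or are ineligible, and treatment length in the extension varies slightly between patients.

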Serum Biochemical Parameters. Blood draws and laboratory analysis will be performed by the Center for Clinical and Translational Science (CCTS). Blood specimens may also be obtained in tubes by the dialysis staff, for pick up by the coordinators, at the time the patient is receiving dialysis to minimize additional patient venipuncture. Serum calcium will be measured using routine laboratory technique (Roche autoanalyzer). Plasma intact and 1-84 PTH levels will be measured by a radioimmunoassay (Scantibodies, Santee, CA). The intra- and interassay coefficients of variation for intact PTH are <5 and <7%, and for 1-84 PTH <6 and <8%. BSAP levels will be measured using an EIA (Metra BAP EIA, Quidel, San Diego, CA). The intra- and inter-assay coefficients of variation are <6% and <8%. TRAP-5b levels will be determined using an EIA (MicroVue, Quidel, Santa Clara, CA). The intra- and inter-assay coefficients of variation are <2.2% and <3%. P1NP levels will be measured using an ELISA (USCNK, Wuhan, China); the intra- and inter-assay coefficients of variation are <9% and <10%. Serum sclerostin levels will be measured using an EIA (Tecomedical group, Sissach, Switzerland). The intra- and inter-assay coefficients of variation are <3.1% and <3.5%. Serum FGF23 levels will be measured by an ELISA (EMD Millipore, Billerica, MA). The intra- and inter-assay coefficients of variation are <8% and <12%. DKK1 will be determined by an ELISA (Biomedica, Vienna, Austria). The intra- and inter-assay coefficients of variation are <8% and <12%. Bone mineral density (BMD) Two techniques—DXA and QCT—will measure BMD. DXA measurements will be performed in the CCTS core facility. QCT measurements will be conducted in the UK Department of Radiology and qualitatively analyzed on a Syngo MMWP workstation and quantified in the Image Analysis Lab of the Division of Nephrology, Bone and Mineral Metabolism. Measurements will be performed using FDA approved imaging equipment, calibration phantoms, and post imaging analysis software/clients used in everyday clinical practice. (The medical center is on a regular schedule of equipment upgrades and, consequently, the specific equipment utilized will change periodically.) Imaging equipment will be maintained and calibrated using manufacturer recommended techniques and schedules. The studies will be performed under the supervision of, and interpreted by, board certified physicians.

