If you are recruiting non-English speaking subjects, the method by which consent is obtained should be in language in which the subject is proficient. Describe the process for obtaining informed consent from prospective subjects in their respective language (or the legally authorized representative's respective language). In order to ensure that individuals are appropriately informed about the study when English is their second-language, describe a plan for evaluating the level of English comprehension, and the threshold for providing a translation, or explain why an evaluation would not be necessary. For additional information on inclusion of non-English speaking subjects, or subjects from a foreign culture, see [IRB Application Instructions for Recruiting Non-English Speaking Participants or Participants from a Foreign Culture](#).

Research Repositories

If the purpose of this submission is to establish a research repository describe the informed consent process. For guidance regarding consent issues, process approaches, and sample language see the Sample Repository/Registry/Bank Consent Template [[PDF](#)]

If interested in the study, patients will be explained all potential risks and benefits by the research coordinators. There are two levels of signed consent. The first will be consent for baseline measurements and the second will be consent for treatment for those who qualify. Upon agreement to participate in the study, patients will not be asked to sign the consent form immediately and will be encouraged to take time to think it over and discuss it as they wish with their primary physician and/or family member. Upon agreement, a written consent form approved by the Institutional Review Board (IRB) will be signed by each patient in the presence of a witness. To avoid the appearance of potential coercion, the PI will not seek consent to participate in the study. He will be available for answering additional questions, if needed, after the informed consent form is signed. One copy of the consent form will be given to the patient, and the original will be stored in the patient's file in the study coordinators' office under lock and key. There will not be emancipated individuals. Only English speaking individuals will be enrolled at this time.

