Safety Precautions: Describe the procedures for protecting against or minimizing any potential risks, *including risks of breach of confidentiality or invasion of privacy*. Where appropriate, discuss provisions for ensuring necessary medical or professional intervention in the event of adverse events, or unanticipated problems involving subjects. Also, where appropriate, describe the provisions for monitoring the data collected to ensure the safety of subjects. If vulnerable populations other than adults with impaired consent capacity are to be recruited, describe additional safeguards for protecting the subjects' rights and welfare.

Initial Consent Patients will be visited by study coordinators while they are on routine dialysis treatment. Patients who meet the inclusion/exclusion criteria will be informed about the goals, procedures, and potential risks of the study treatment modalities. It will be emphasized that willingness or unwillingness to participate in any aspect of the proposed studies will not affect the patients' medical care. The protocol will be presented by the study coordinator supported by the PI where needed and the patients will be given ample time to think about their participation and to discuss participation with their primary nephrologist, other treating physicians, or any other persons. After verbal agreement to participate, a written first consent form approved by the IRB of the University of Kentucky will be

signed by each patient. Consented patients will have BMD measurements of the total hip, lumbar spine, radius and whole body scan by DXA. We do not perform QCT measurements at this time in order to avoid unnecessary radiation exposure to patients who are not osteoporotic by DXA T-scores at any site because they will not participate any further in the study. Those patients who are identified as having low bone density/osteoporotic will have blood draws performed for determination of bone turnover status and for baseline values of biochemical tests used for monitoring. They will also have BMD measurements of their total hip and spine by QCT, and CAVC measured by MDCT.

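### Baseline QCT and MDCT are described as done before treatment consent is sought, so patients lost at that step have CT scans that serve no between-group endpoint

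*Combined protocol and SAP*

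**What the plan says.** The Informed Consent Process section describes two consents ahead of the later extension consent: "The first will be consent for baseline measurements and the second will be consent for treatment for those who qualify".

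Safety Precautions, under Initial Consent, sets out what follows the first signature. DXA comes first. Patients with low bone density then have bloods for turnover status and baseline biochemistry, and the paragraph goes on: "They will also have BMD measurements of their total hip and spine by QCT, and CAVC measured by MDCT". The next paragraph, Treatment Consent, opens: "Once bone turnover status has been determined, patients will be approached for the second consent form addressing treatment". Research Procedures gives the same order: DXA, then bloods with QCT and MDCT, then assignment to a turnover arm and randomisation.

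On radiation, Research Procedures says "We do not use QCT for initial BMD assessment to avoid unnecessary radiation exposure to patients with normal bone mass who will be excluded". Initial Consent says "We do not perform QCT measurements at this time in order to avoid unnecessary radiation exposure to patients who are not osteoporotic" on DXA, and gives the reason: "because they will not participate any further in the study".

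On blood sampling, Study Design (Serum Biochemical Parameters) allows a route that needs no hospital visit: "Blood specimens may also be obtained in tubes by the dialysis staff".

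**The concern.** The plan withholds CT until DXA has removed people who will not continue. The next point at which people can leave is treatment consent, when they are asked to accept study drug or randomisation to no study treatment. As described, CT falls before that point. Someone who refuses there, or is found ineligible from results arriving at that stage, has had a QCT and an MDCT. Those scans cannot contribute to the comparison of treatment with control in BMD or calcification change.

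What is at stake is avoidable radiation to people who never enter the randomised comparison. The plan itself takes CT exposure seriously. Study Population excludes anyone with more than three CT scans in the prior 12 months, and Potential Risks says each CT gives more than typical natural background exposure. The validity of the primary analysis is not at stake.

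**Working it through.** **1. Does anything before randomisation need a CT result?** Research Procedures bases turnover status on PTH, the PTH ratio and TRAP-5b, all blood tests. Low bone density is judged on DXA. The adaptive randomisation uses group completion rates, age, race and gender. No inclusion or exclusion criterion uses a study CT finding. CT is needed only as the baseline for change, so it must precede treatment but need not precede treatment consent.

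**2. How far does the stated avoidance reach?** Research Procedures limits it to normal bone mass, and Initial Consent to patients who are not osteoporotic by DXA. DXA followed by CT satisfies both. The reason given, that these patients take no further part, is equally true of those who decline treatment consent.

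**3. Can ineligibility surface this late?** Normal corrected calcium is an inclusion criterion, and serum calcium is in the same baseline draw as the turnover bloods, so it is possible. It is not established, because calcium is also recorded from medical records and the draw is not called an eligibility test. Two exclusions (radius T-score and prior skeletal radiation) apply only if the patient is randomised to teriparatide. The radius value is already known from the DXA, and prior radiation would ordinarily be known from the history.

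**4. How many reach CT?** Research Procedures expects 30% or 178 patients to leave at DXA, out of 990 consented. These figures do not agree:

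- 0.30 × 990 = 297, not 178
- 178 / 990 = 18.0%
- 178 / 0.30 = 593, so the count fits a total of about 593

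Three readings of the number reaching CT follow:

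- 30% excluded: 990 × 0.70 = 693
- 178 excluded: 990 − 178 = 812
- only 30% qualify (the Background figure for osteoporosis): 990 × 0.30 = 297. This is a low case, since the current criterion is low bone density.

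**5. How many are scanned without entering?** The documents give no rate of refusal or late ineligibility. For an assumed loss rate r, the number is (patients reaching CT) × r:

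| Reaching CT | 5% | 10% | 20% | 30% |
|---|---|---|---|---|
| 297 | 15 | 30 | 59 | 89 |
| 693 | 35 | 69 | 139 | 208 |
| 812 | 41 | 81 | 162 | 244 |

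The span is 15 to 244.

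**The case against.** The strongest reply is that nothing in the plan is broken. A reader might infer that these patients receive radiation the plan says it avoids. The text does not support that, because the promise covers only people who fail the DXA screen. A reader might also infer that the CT is done without consent. It is not: it falls under a signed consent for baseline measurements. The consent forms are not in the reviewed text, so their CT wording cannot be checked.

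The order itself is inferred from the sequence of description. The Treatment Consent paragraph ties the second consent to turnover status, not to completed CT, and the flow attachments are not in the text. Practice may already defer CT. That limits how firmly the point can be put, but no section makes CT wait.

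The loss rate is also an assumption. Initial Consent says the risks of the study treatments are explained before the first signature, so some unwilling patients would leave before any scan. This argues for the lower end of the range. It does not remove refusals at the second consent, which the plan stresses patients are free to make.

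On cost, Payment gives $150 per scan visit. If DXA and CT now share a day, separating them adds a paid visit for each continuing patient. With 693 reaching CT and 5-30% loss, that is at most 485 to 658 visits (693 − 208 and 693 − 35). A claim of fewer payments overall therefore cannot be made. Whether the scans share a day is not stated, although Initial Consent says QCT is not performed at the DXA stage.

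Finally, a reader might infer that scanning before the decision period distorts the one-year endpoint. Research Procedures allows 1-2 weeks for deciding on participation, which is 2-4% of a year (1/52 to 2/52). The gap precedes randomisation, so it affects both groups alike. The effect is negligible.

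**Conclusion.** The point holds as a cheap design improvement. As written, baseline QCT and MDCT precede treatment consent although no step before randomisation needs their results. The plan's own reason for withholding CT is not carried through to the next point of loss. This is a gap in applying a rationale, not a contradiction.

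The size is uncertain: roughly 15 to 244 people scanned without entering. That rests on an assumed 5-30% loss and on a number reaching CT that the plan's inconsistent 30% or 178 leaves anywhere from about 297 to 812. Refusal is the likelier source of loss; late ineligibility is possible but not shown. The conclusion also assumes that practice follows the order of description.

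**What to change.** State one order in Research Procedures and in the Initial Consent and Treatment Consent paragraphs of Safety Precautions:

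1. DXA
2. Turnover and eligibility bloods, which dialysis staff may draw
3. Treatment consent, once turnover is known
4. QCT and MDCT
5. Randomisation
6. Start of treatment

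Keeping treatment consent after the turnover result lets the discussion concern the drug that applies to that patient. Both scans still precede randomisation, so no baseline data for the endpoints are lost. If CT is already deferred in practice, the text need only say so.

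The cost is protocol wording, with matching consent-form wording where the forms describe the CT. If DXA and CT are currently done on one day, some continuing patients may need a separate CT visit, with its $150 payment and mileage. Separately, the 30% or 178 figure should be reconciled with 990, so that the number of patients expected to reach CT is known.
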